### **5.12.3. Type 1 Error Rate Control Strategy for Primary and Key Secondary Efficacy Analysis.**

Since they are intended for different purposes, no type 1 error rate adjustments will be made for conducting analysis relative to “efficacy” and “treatment-regimen” estimands. For analysis within each estimand, type 1 error rate control strategy for evaluation of primary and key secondary objectives is illustrated in [Figure GPGM.5.1](#).

As illustrated in the figure,

1.  $H_{15,1}$ ,  $H_{15,2}$ , and  $H_{15,3}$  are evaluated hierarchically each at two-sided 0.025 significance level conditioned on the successfully achieving the preceding objective. In parallel,
2.  $H_{10,1}$ ,  $H_{10,2}$ , and  $H_{10,3}$  are evaluated hierarchically each at two-sided 0.025 significance level conditioned on the successfully achieving the preceding objective.
3.
  - a) If all objectives in #1 and #2 above are successfully established,  $H_{5,1}$ ,  $H_{5,2}$ , and  $H_{5,3}$  are evaluated hierarchically, each at two-sided 0.05 significance level.

- b) If all objectives in only #1 or only #2 above are successfully established,  $H_{5,1}$ ,  $H_{5,2}$ , and  $H_{5,3}$  are evaluated hierarchically, each at two-sided 0.025 significance level.
4. If all objectives:  $H_{5,1}$ ,  $H_{5,2}$ , and  $H_{5,3}$  are successfully established and
- a) if all objectives in #1 and #2 above are successfully established, then  $H_{10,4}$ ,  $H_{15,4}$  and  $H_{5,4}$  will be evaluated hierarchically each at two-sided 0.05 significance level conditioned on the successfully achieving the preceding objective.
  - b) if all objectives in only #1 or only #2 above are successfully established, then  $H_{10,4}$ ,  $H_{15,4}$  and  $H_{5,4}$  will be evaluated hierarchically each at two-sided 0.025 significance level conditioned on the successfully achieving the preceding objective.
5. If all objectives in #3 and #4 above are successfully established, and at least 1 objective from #1 or #2 above is not successfully established, recycle 100% of the unused alpha back to #1 or #2 above.

**Figure GPGM.5.1. Type 1 Error control strategy for primary and key secondary efficacy endpoints.**

#### 5.12.4. Other Secondary and Exploratory efficacy Analyses

Other secondary and Exploratory efficacy measures will be summarized by treatment and nominal visit. Statistical analyses will be conducted in a manner similar to Sections 5.12.1 and 5.12.2. However, missing data will not be imputed and assessments are not subject to type 1 error rate control.

Objective	Relative to the efficacy measure:	Analysis Conducted in a manner similar to:	Additional Information
QW tirzepatide 5 mg, 10 mg, and/or 15 mg is superior to insulin glargine at 52 weeks	Change from baseline in fasting serum glucose	5.12.1	Use baseline HbA1c strata as a fixed effect in place of baseline HbA1c as a covariate. Use baseline FSG as a covariate. LSM estimates will be plotted by treatment and visit.
	Change from baseline in 7-point self-monitored blood glucose (SMBG) profiles	5.12.1	Use baseline HbA1c strata as a fixed effect in place of baseline HbA1c as a covariate. Use baseline SMBG as a covariate. LSM estimates at 52-weeks will be plotted by treatment and 7-points.
	proportion of patients achieving an HbA1c target value of $\leq 6.5\%$ (48 mmol/mol),	5.12.2.3	None
	proportion of patients achieving an HbA1c target value of $< 5.7\%$ (39 mmol/mol).	5.12.2.3	None
	proportion of patients who achieved weight loss of $\geq 5\%$ , from baseline	5.12.2.3	Use baseline HbA1c strata as a fixed effect in place of baseline HbA1c as a covariate and baseline weight as a covariate
	proportion of patients who achieved weight loss of $\geq 10\%$ from baseline	5.12.2.3	Use baseline HbA1c strata as a fixed effect in place of baseline HbA1c as a covariate and baseline weight as a covariate
	proportion of patients who achieved weight loss of $\geq 15\%$ from baseline	5.12.2.3	Use baseline HbA1c strata as a fixed effect in place of baseline HbA1c as a covariate and baseline weight as a covariate
To compare tirzepatide 5 mg, 10 mg, and 15 mg to insulin glargine at 52 weeks	Change from baseline in waist circumference	5.12.1	Use baseline HbA1c strata as a fixed effect in place of baseline HbA1c as a covariate. Use baseline waist circumference as a covariate.
	Change from baseline in lipid parameters (Total-Cholesterol, HDL, VLDL, TG)	5.12.1	Use baseline HbA1c strata as a fixed effect in place of baseline HbA1c as a covariate. Use corresponding

			baseline lipid parameter as a covariate.
To characterize long-term (beyond 52 weeks) glycemic control with tirzepatide 5 mg, 10 mg, and 15 mg	Change from baseline in HbA1c	5.12.1	The analysis will be conducted utilizing HbA1c data from baseline through the end of efficacy follow-up
QW tirzepatide 5 mg, 10 mg, and/or 15 mg is superior to insulin glargine at 52 weeks	Proportion of patients achieving HbA1c target $\leq 6.5\%$ and without weight gain ( $<0.1$ kg) and without documented symptomatic hypoglycemia or severe hypoglycemia	5.12.2.3	Include rate of hypoglycemic events at baseline and baseline body weight as additional covariates
	Proportion of patients achieving HbA1c target $< 7.0\%$ and without weight gain ( $<0.1$ kg) and without documented symptomatic hypoglycemia or severe hypoglycemia	5.12.2.3	Include rate of hypoglycemic events at baseline and baseline body weight as additional covariates
	Proportion of patients achieving HbA1c target $\leq 6.5\%$ and without weight gain ( $<0.1$ kg) and without clinically significant documented symptomatic hypoglycemia or severe hypoglycemia	5.12.2.3	Include rate of hypoglycemic events at baseline and baseline body weight as additional covariates
	Proportion of patients achieving HbA1c target $< 7.0\%$ and without weight gain ( $<0.1$ kg) and without clinically significant documented symptomatic hypoglycemia or severe hypoglycemia	5.12.2.3	Include rate of hypoglycemic events at baseline and baseline body weight as additional covariates

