### 5.4. Handling of Dropouts or Missing Data

For the primary and key secondary efficacy endpoint analyses subject to type 1 error rate control, data for patients with missing values at the 52-week visit will be imputed based on the method describe in Section 5.12.1.3. Unless specified otherwise, imputation of missing data will be limited to primary and key secondary efficacy endpoint analysis. Missing other secondary or exploratory efficacy parameter values and missing safety laboratory values will not be explicitly imputed.

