## 5.12. Efficacy Analysis

For the FDA and potentially for other regulatory agencies, all efficacy assessments will be guided by the “treatment-regimen” estimand conducted using FAS. Assessment of the primary and secondary efficacy objectives subject to type 1 error rate control (key secondary) will be conducted with multiple imputation of missing data (see Section 5.12.1.3) at 52 weeks.

Assessment of other efficacy objectives will be conducted without imputation of missing data. For publications and other purposes, the assessment of efficacy objectives will be guided by the “efficacy” estimand using EAS set without imputation of missing data. A listing of patients randomized but not included in efficacy analyses (ie, not treated, discontinued treatment due to inadvertent enrollment) will be provided.

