#### **5.12.1.3. Methods for Multiple Imputations**

For efficacy analysis relative to “treatment-regimen” estimand, missing HbA1c data at the 52-week visit will be imputed based on “retrieved dropouts,” defined as patients who had their HbA1c value measured at the 52-week visit in the same treatment arm who prematurely discontinued study drug. If the imputed value of HbA1c change from baseline is  $< -6.0\%$  or  $> 6.0\%$ , that value will be set to  $-6.0\%$  or  $6.0\%$ , respectively, to avoid unrealistic imputed values.

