#### **5.12.2.2. Mean change in body weight from baseline at the 52 week visit**

The analysis for change in body weight from baseline (postbaseline - baseline) will be conducted in a manner similar to the primary analysis in Section 5.12.1. Baseline HbA1c concentration ( $\leq 8.5\%$ ,  $> 8.5\%$  [ $\leq 69$ ,  $> 69$  mmol/mol]) will be used as a fixed factor in place of baseline HbA1c as a covariate and baseline body weight will be used as an additional covariate in the statistical

model. Least Squares Mean (LSM) estimate of mean change in body weight from baseline will be plotted by nominal visit and by study treatment. For multiple imputation of missing values, if the imputed value of weight change from baseline is  $<-50$  kg or  $>50$  kg, then that value will be set to  $-50$  kg or  $50$  kg, respectively, to avoid unrealistic imputed values.

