### **5.12.2.3. Proportion of Patients Achieving HbA1c $<7\%$ at the 52 week Visit**

The analysis relative to the “efficacy” estimand for the endpoint at 52 weeks will be conducted using EAS with missing values imputed from an MMRM model and then dichotomized. The MMRM model includes country/pooled country, SGLT2 inhibitor use at baseline, treatment, visit, and treatment-by-visit interaction as fixed effects, and baseline HbA1c as a covariate. After dichotomizing continuous HbA1c, the data is analyzed using a logistic regression model with treatment, country/pooled country, SGLT2 inhibitor use at baseline, and baseline HbA1c as a covariate. In addition, analysis will be conducted utilizing data using EAS from baseline through the 52-week visit with the aid of a longitudinal logistic regression with repeated measurements with country/pooled country, SGLT2 inhibitor use at baseline, treatment, visit, treatment-by-visit interaction as fixed effects, and baseline HbA1c as a covariate. In the case that longitudinal logistic model does not converge due to small number of events, logistic regression will be utilized to analyze proportion of patients achieving HbA1c $<7\%$  at nominal visits.

Analysis relative to “treatment-regimen” estimand will be conducted utilizing HbA1c data in FAS at baseline and at the 52-week visit with the aid of a logistic regression with multiple imputation of missing HbA1c data at the 52-week visit (see Section 5.12.1.3 for details). Model terms will include treatment, country/pooled country, SGLT2 inhibitor use at baseline as fixed effects, and baseline HbA1c as a covariate and statistical inference over multiple imputations will be guided by Rubin (1987).

[figure not shown]

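### Under the treatment-regimen estimand, missing Week-52 HbA1c and weight are imputed for the primary and key secondary analyses but dropped for HbA1c ≤6.5%, HbA1c <5.7% and weight loss ≥5/10/15%

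*SAP*

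**What the plan says.** The no-imputation rule appears in three places in the SAP.

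- Section 5.4: "Unless specified otherwise, imputation of missing data will be limited to primary and key secondary efficacy endpoint analysis".
- Section 5.12, following the treatment-regimen analyses intended for the FDA: "Assessment of other efficacy objectives will be conducted without imputation of missing data".
- Section 5.12.4, for the other secondary and exploratory measures: "However, missing data will not be imputed and assessments are not subject to type 1 error rate control". The table there lists HbA1c ≤6.5%, HbA1c <5.7% and weight loss ≥5%, ≥10% and ≥15%, and sends all five to Section 5.12.2.3 for the method.

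The underlying variables are imputed elsewhere under the treatment-regimen estimand.

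- Section 5.12.1.3: "missing HbA1c data at the 52-week visit will be imputed based on" retrieved dropouts, meaning patients in the same arm who stopped study drug early but were measured at Week 52.
- Section 5.12.2.2, for body weight: "For multiple imputation of missing values, if the imputed value of weight change from baseline is" outside ±50 kg, it is truncated to that limit.
- Section 5.12.2.3, for HbA1c <7%: a "logistic regression with multiple imputation of missing HbA1c data at the 52-week visit".

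For the efficacy estimand, Section 5.12.2.3 gives two analyses of HbA1c <7%. One is "conducted using EAS with missing values imputed from an MMRM model and then dichotomized". The other is a longitudinal logistic regression over all visits to Week 52, with visit-wise logistic regression if it fails to converge because events are few.

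**The concern.** Given the baseline values, the five responder endpoints are thresholds of Week-52 HbA1c and weight, and under the treatment-regimen estimand the plan already fills in both when they are missing. By imputing from patients who stopped drug, the plan takes the view that patients without a Week-52 value resemble off-drug patients in the same arm. A Week-52 logistic regression on observed cases takes another view: given treatment and the other model terms, missing patients resemble those observed. One report would hold both views about the same missing value.

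Two things are at stake. The responder rates and their differences may be biased. In addition, the HbA1c <7%, ≤6.5% and <5.7% rates would not share a denominator, so the gaps between them could not be read as the share of patients lying between two cut-offs.

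**Working it through.** **1. The plan's own figure.** No power or sample size is given for the responder endpoints. The nearest figure is 90% power for HbA1c superiority (Protocol 10.1: 313 vs 939 patients, difference 0.30, SD 1.3, two-sided alpha 0.025).

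- SE = 1.3 × √(1/939 + 1/313) = 0.0848.
- 0.30/0.0848 − 2.241 = 1.29, which gives power 0.902.

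The figure reproduces and does not depend on this point.

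**2. Which analysis is left for the five endpoints.** Section 5.12.4 sends them to 5.12.2.3 but removes imputation.

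| 5.12.2.3 analysis | Data set | After the 5.12.4 rule |
|---|---|---|
| MMRM-imputed, then logistic | EAS | Imputation removed: Week-52 observed cases |
| Longitudinal logistic | EAS, all visits | Unchanged: needs no imputation |
| Multiply imputed logistic | FAS, Week 52 | Imputation removed: Week-52 observed cases |

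Only the third row serves the treatment-regimen estimand. For that estimand the results are therefore complete-case at Week 52.

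**3. Size of the discrepancy.** Let m be the missing fraction in an arm, p the response rate among observed patients and q the rate among missing patients.

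- Rate including missing patients = (1 − m)p + mq.
- Error of the complete-case difference = m_T(p_T − q_T) − m_G(p_G − q_G), with T for tirzepatide and G for glargine.

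The documents give none of these inputs, so all values are assumptions. With p = 60% and q = 25% on tirzepatide, and p = 30% and q = 15% on glargine, the complete-case difference is always 30.0 points:

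| Missing T / G | T rate | G rate | Difference | Complete-case error |
|---|---|---|---|---|
| 5% / 5% | 58.25% | 29.25% | 29.0 | +1.0 |
| 10% / 10% | 56.5% | 28.5% | 28.0 | +2.0 |
| 15% / 5% | 54.75% | 29.25% | 25.5 | +4.5 |
| 5% / 15% | 58.25% | 27.75% | 30.5 | −0.5 |
| 28% / 28% | 50.2% | 25.8% | 24.4 | +5.6 |

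A second assumed set has 70% observed and 30% missing response on tirzepatide, and 30% and 20% on glargine:

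- 5%/5% missing: 0.05 × 40 − 0.05 × 10 = +1.5 points.
- 8%/6% missing: 3.2 − 0.6 = +2.6 points.
- 12%/8% missing: 4.8 − 0.8 = +4.0 points.

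The 28% row is an extreme. Protocol 10.1 uses 28% as a ceiling on rescue or study-drug discontinuation, and patients who stop drug are to stay in the study, so FAS missingness should be lower. These are crude proportions, whereas the planned model adjusts for covariates.

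**4. Efficacy estimand.** If the longitudinal model fails and the visit-wise fallback is used, and if all of the 28% lack a Week-52 EAS value, the analysis has 313 × 0.72 ≈ 225 patients per tirzepatide arm and 939 × 0.72 ≈ 676 on glargine. About 88 and 263 patients are dropped.

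**The case against.** The rule is explicit and stated consistently in three sections, so it is a deliberate choice. The endpoints are outside type 1 error control, and SAP 3.3 calls them exploratory. No confirmatory claim, alpha or power depends on them. This stands, and it limits the severity. It does not explain why one missing value should be handled in two ways within one estimand. SAP 5.12 applies the treatment-regimen estimand to all efficacy assessments for the FDA, so these endpoints fall under it.

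A reader might infer several stronger points that the documents do not support.

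- *That the responder results are complete-case throughout.* Under the efficacy estimand, the longitudinal logistic model uses all EAS visits. It gives way to a Week-52 analysis only through the convergence fallback, which is plausible for rare outcomes such as HbA1c <5.7% or weight loss ≥15%.
- *That imputed data sets exist for both estimands.* Under the efficacy estimand, mean weight change is analysed by MMRM without imputation, and no number of imputations is stated for the MMRM-imputed HbA1c <7% analysis.
- *That dropping these patients contradicts the estimand.* FAS keeps Week-52 values obtained after drug discontinuation or rescue. Only patients with no Week-52 value are lost, so the issue is the missing-data assumption made within the estimand.
- *That missing patients are mostly those who left, and that the bias must favour tirzepatide.* SAP 5.20.4 anticipates primary-endpoint visits missed because of COVID-19, which need not reflect response. Missingness is also limited by the widened Visit 24 window and home visits (Protocol Appendix 8), and for HbA1c by local-laboratory and unscheduled values (SAP 5.12.1). Equal gaps between observed and missing response with equal missingness give zero error in the difference, and one scenario above is negative.

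**Conclusion.** The point holds for the treatment-regimen estimand. SAP 5.4, 5.12 and 5.12.4 leave HbA1c ≤6.5%, HbA1c <5.7% and the three weight-loss thresholds as Week-52 complete-case analyses, while HbA1c <7% and the mean changes in HbA1c and weight include imputed patients. The inconsistency is certain from the text. The bias is not: its sign and size are unknown, and the range of about −0.5 to +5.6 points rests on assumed response and missing rates, with the upper end at a missing rate that FAS is unlikely to reach.

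Under the efficacy estimand there is a lesser problem of clarity. Section 5.12.4 cites a section with more than one analysis and then withdraws the imputation that one of them needs. Section 5.12 also describes efficacy-estimand assessments as free of imputation, although 5.12.2.3 imputes from an MMRM. This should be made right as an inexpensive improvement of modest importance.

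**What to change.** - **Treatment-regimen estimand.** In 5.4, 5.12 and 5.12.4, exempt endpoints that are thresholds of Week-52 HbA1c or body weight from the no-imputation rule. Dichotomise the multiply imputed HbA1c data sets at ≤6.5% and <5.7%, and the imputed weight data sets at ≥5%, ≥10% and ≥15% loss. Fit the 5.12.2.3 logistic model with the covariates in the 5.12.4 table and pool by Rubin's rules.
- **Efficacy estimand.** State which 5.12.2.3 analysis applies to these five endpoints, and reconcile the wording of 5.12 with the MMRM-based imputation in 5.12.2.3.
- **Unchanged.** Leave fasting serum glucose, SMBG, waist circumference and lipids as planned. The four HbA1c, weight and hypoglycaemia composites in 5.12.4 are not settled by this change, because their hypoglycaemia component is not imputed.

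The cost is SAP wording and a few lines of code on data sets the plan already creates. For the treatment-regimen estimand it needs no new data and no new imputation model.

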### 5.13. Safety Analysis

Unless specified otherwise, safety assessments will be based on the Safety analysis Set (see [Table GPGM.5.1](#)). All events that occur between the date of first dose of study drug to the date of patient's safety follow-up visit or patient's end of study participation will be included, regardless of the adherence to study drug or initiation of rescue therapy. For assessing benefit and risk profile through 52-weeks, selected safety analyses will be conducted by utilizing safety data from first dose through the date of 52 week visit. Some safety analysis may be conducted after excluding data after the initiation of new antihyperglycemic therapy. Unless specified otherwise, statistical assessment of homogeneity of the distribution of categorical safety responses among treatment arms will be conducted using Fisher's exact test.

Unless specified otherwise, difference among treatment mean change from baseline in continuous safety parameters at all scheduled visits will be assessed via a MMRM using REML. The model will include country/pooled country, baseline HbA1c ( $\leq 8.5\%$ ,  $> 8.5\%$  [ $\leq 69$ ,  $> 69$  mmol/mol]), baseline SGLT2 inhibitor use (Yes or No), treatment group, visit, and treatment-by-visit interaction as fixed effects, and baseline value of the safety parameter as a covariate. To model the covariance structure within patients, the unstructured covariance matrix will be used. If this model fails to converge, the following covariance structures will be tested in order specified in Section 5.12.1.1.

For selected safety parameters, time-to-first-event analysis via Cox proportional hazards model may be conducted. For patients without event, “time-to-event” will be censored as time (in days) from first dose to end of study participation (date of death, study discontinuation, or date of safety follow-up). For patients experiencing the event, “time-to-first-event” will be the time (in days) from first dose to first occurrence of the event.

Where necessary, rate of events will be analyzed using a generalized linear mixed-effects model assuming the number of events follow a negative binomial distribution, treatment as a fixed effect. The logarithm of days during analysis interval will be adjusted as an offset to account for possible unequal treatment duration of follow-up between patients.

### **5.13.1. Adverse Events**

A listing of AEs occurring either before first dose or after patient’s last date of study participation will be provided. Listing will include patient identification including the treatment, site number, event information: AE group ID, event start date, MedDRA System Organ Class (SOC), and Preferred Term (PT), seriousness, severity, outcome, relationship to study drug, time from first dose of study drug to the event, time from last dose of study drug to event, and time from end of study participation to the event.

A TEAE is defined as an event that first occurred or worsened in severity after baseline. The MedDRA Lowest Level Term (LLT) will be used in the treatment-emergent derivation. The maximum severity for each LLT during the baseline period including ongoing medical history will be used as baseline severity. For events with a missing severity during the baseline period, it will be treated as ‘mild’ in severity for determining treatment-emergence. Events with a missing severity during the postbaseline period will be treated as ‘severe’ and treatment-emergence will be determined by comparing to baseline severity.

The percentages of patients with TEAEs will be summarized by treatment using MedDRA PT nested within SOC. Statistical comparisons will be applied at both the SOC and PT levels. Events will be ordered by decreasing frequency within SOC. For events that are sex-specific, the denominator and computation of the percentage will include only patients from the given sex.

Overview of the number and percentage of patients who experienced a TEAE, serious adverse event (SAE), death, discontinued from study treatment, or study due to an AE, and relationship to study drug, will be summarized by treatment.

The percentages of patients with TEAEs, overall and common (common TEAEs occurred in  $\geq 5\%$  of any treatment arm before rounding of treated patients), will be summarized by treatment using MedDRA PT. Events will be ordered by decreasing frequency.

The percentages of patients with TEAEs by maximum severity will be summarized by treatment using MedDRA PT. For each patient and TEAE, the maximum severity for the MedDRA PT is the maximum postbaseline severity observed from all associated LLTs mapping to the MedDRA PT. The maximum severity will be determined based on the non-missing severities. If all severities are missing for the defined postbaseline period of interest, it will show as missing in the table. Only counts and percentages will be included for the TEAEs by maximum severity.

Patient narratives will be provided for all patients who experience any of the following events:

- Deaths
- SAEs
- Permanent discontinuations of study treatment due to AEs
- Severe adverse events of special interest

